Most studies that have evaluated accommodative ability and function while wearing soft multifocal contact lenses have examined center distance lenses. Because center distance lenses are used for myopia management, the interest has been to determine if children maintain normal accommodative function while wearing the lenses.

Accommodative function while wearing center near lenses has likely not been studied often because these lens designs are used most in presbyopic populations who have no or waning accommodative ability and are using the lenses, specifically, to account for that accommodative inability.-Knowing how spectacle lenses with add powers effectively treat some binocular vision and accommodative disorders and understanding how center near multifocal contact lenses correct presbyopic vision, it is reasonable to hypothesize that center near multifocal contact lenses may provide a greater therapeutic effect for accommodative and binocular vision disorders than center near designs because the central portion of the lens is the addition power, unlike the center-distance lens designs. This study will aim to determine how accommodative function varies with center distance and center near multifocal contact lenses.

Procedures:

Research Design

This study will be an observational single-center investigation using a cross sectional design and each subject will undergo two test sessions.

Sample

The sample size necessary for this study is 20 subjects. The sample size calculation was completed using effect size with standard deviation values from previously published objective accommodative difference between center-distance multifocal contact lenses and single vision contact lenses, which found about $1.0\text{ D} \pm 0.53\text{ D}$ difference (Gong et al., 2017). In order to detect a 0.5 D difference in accommodative amplitude between center-distance and center-near contact lenses with 90% statistical power, a sample of 14 participants is required. Because a study investigating this hypothesis has not been performed in the past, we will enroll an additional 6 patients to account for unknown variability in the data.

Eligibility Criteria are:

- Ages 18 to \leq 30 years old
- Acuity of 20/25 or better in both eyes with habitual contact lens prescription
- No history of ocular disease or active ocular inflammation
- No history of ocular or refractive surgery
- No current history of rigid contact lens wear
- Astigmatism \leq 1.00 D

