- Free of binocular vision disorder (strabismus, amblyopia, vergence dysfunction, accommodative dysfunction)
- No prior or concurrent participation in myopia control or use of low dose atropine, multifocal contact lenses
- No use of any medications suspected to affect accommodation

If a subject presents with conditions such as uncorrected refractive error or pathology, an appropriate referral will be made.

Potential participants will be recruited in the following manners:

- Word of mouth by the investigators among employees and visitors to the College of Optometry
- Flyers
- Email announcements distributed to the faculty, staff, and students at OSU
- Electronic advertisement in the OSU Healthbeat
- Phone calls to potentially eligible participants who are identified from a review of clinical records at the College of Optometry to identify those who wear soft contact lenses.

Measurement

The primary measurement of interest is accommodation, which will be quantified using the following techniques:

Objective Accommodative Amplitude: This non-invasive technique quantifies the total focusing ability of the eye using methods that are commonly used clinically. The refractive power of the eye will be measured with the Grand Seiko autorefractor (a commercially available instrument) while study participants view a 20/30 sized letter at multiple stimulus positions (ranging from optical infinity to 20cm). Ten repeated measures will be collected at each stimulus position. For all measurements, participants will wear an eye patch over their left eye and view the letter target with their right eye while keeping their chin in a chinrest and forehead against the forehead rest. The Grand Seiko autorefractor uses infrared light to obtain refractive measures of the eye and the procedure is non-invasive. The following distances are where accommodation will be assessed: 2.5 D (40 cm), and 4 D (25 cm), and 5 D (20 cm). Because multifocal contact lenses can interfere with the optics and readings of an autorefractor, the multifocal will only be worn on the left eye during this testing. The patient's habitual

contact lens with distance only will be on the right eye. An infrared wratten filter will be placed over the right eye, so that the left eye (with the multifocal) will influence accommodation and readings can be obtained from the right eye.

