Subjective Accommodative Amplitude: This technique quantifies the nearest position of clear focus using a method that is the standard technique used in a routine eye examination whereby the participant will be asked to view a row of 20/30 letters first held in close proximity to the eye (approximately 2-3 cm) and then pulled away from the eye along a near point rod. The participant will be instructed to report the moment when the letters first become blurred. The measurement will be repeated three times and averaged and the individual findings compared to published age norms for classification of reduced or adequate accommodative amplitude (Hofstetter, 1944).

Accommodative Accuracy: This technique determines the accuracy of the eye to focus at a near viewing distance. A handheld light and loose trial spectacle lenses are used to quantify the focusing position of the eye while the participant views letters printed on a card. The lenses are held in front of the participant's eye and the light shown quickly across the eye from arm's length.

Accommodative Facility: This technique determines the ability of the eye to quickly focus and relax, which is often needed for visual demands in a classroom. Participants will view a 20/30 letter at 40 cm. The examiner will then place ± 2.00 D flipper lenses in front of the patient's eye (plus or minus). Once the participant clears the letters, they will state "clear" and the examiner will flip to the other side. The number of flips per minute will be recorded.

Detailed Study Procedures

The study will enroll 20 participants from 18-30 years old. The study consists of two days of office visits to the OSU College of Optometry (a baseline visit, and then a second visit on another day with center-distance and center-near contact lenses). Participants will complete the study visits in the Fry Hall clinic research Lab.

Baseline Exam:

- Questions regarding participant demographics, medical history, ocular history, medication use, and refractive error (glasses and contacts) if known.
- Visual Acuity – participants identifying letters to assess visual acuity at distance and near.
- Contrast Sensitivity – participants identifying letters to identify contrast sensitivity at 50 cm.
- Pupil Size – determination of pupil size using a ruler to measure diameter in millimeters in light and dark.
- Ocular alignment:

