 - Cover Test - participants viewing a letter or picture while an investigator covers the eyes with a cover paddle and assessed eye alignment.

- Modified Thorington - Measured at distance and near.
- Near Point of Convergence – participants viewing letters while they are moved closer to the eyes to assess convergence movements.
- Stereopsis – participants wearing 3D glasses and identifying shapes in a book to assess depth perception.
- Accommodation - Measures of accommodation will be performed in the following order using the protocols described above under “Measurements”:
 - **Push-up method** - Accommodative amplitudes of accommodation will be measured in the right eye only, 3 times.
 - **Monocular estimation method (MEM)** - This will be measured at 40 cm, in the right eye only.
 - **Accommodative Facility** - Accommodative facility (in cycles/minute) will be measured with ± 2.00 D flippers in the right eye only and binocularly.
 - **Grand Seiko WR-5100K** – Refractive Error will be measured at several points:
 - 0 D (distance)
 - 2.5 D (40 cm)
 - 4 D (25 cm)
 - 5 D (20 cm)
- Refractive Error Assessment – Non-cycloplegic central refractive error (with and without contact lenses). Non-cycloplegic refractive error will be assessed with the Grand Seiko WR-5100K. This will be done with and without Biofinity sphere contact lenses (that is the same prescription as the participant’s habitual contact lens prescription). An average of 10 readings will be calculated (both with and without habitual correction).
- Dilation – participants will be dilated with 1% tropicamide. They will receive 2 drops, 5 minutes apart.
- Cycloplegic Central Refractive Error (without contact lenses). Cycloplegic refractive error will be assessed with the Grand Seiko WR-5100K. This will be done without contact lenses on. An average of 10 readings will be calculated.

Second Visit

- At the second visit, participants will repeat measurements completed at the first examination (except for dilation/cycloplegia) with a center-distance and center-near Biofinity multifocal contact lens (both with +2.50 D add). The order will be randomized for each participant. The multifocals will be worn binocularly for all testing except for autorefraction, so that the optics of the contact lenses will not interfere with measurements.

The total time for each study visit will be no more than 90 minutes.

Study Risks

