The risks involved with the participation of this study are no greater than that incurred in a routine eye exam with dilation. The side effects that participants might experience are blurred vision (that generally affects near viewing more than distance), and light sensitivity. Previous studies suggest that the side effects of both concentrations are minimal and do not impede activities of daily living. These drops will only be instilled one time at one visit and side effects should wear off within 4-6 hours. All other study procedures are non-invasive and only involve lights as the participant places his/her chin on a chinrest and looks straight ahead.

Data Collection and Participant Confidentiality

Data will be collected on a paper study form that includes only the participant's study ID. Study measures obtained with the autorefractor will be printed from the instrument and the participant's study ID written on the print-out. The print-outs will then be taped to the paper study form and later scanned into pdf format for storage on the Investigator's computer. No personally identifying information will be stored on the paper datasheet, or in the generation of the scanned pdf. Signed consent/assent/parental permission documents will be kept separate from the study data sheet in a binder in the Investigator's locked laboratory, accessible only to the study team. The link between the study ID and the participant's personal information will be maintained on the signed consent documents.

Internal Validity

There are no threats to internal validity. All procedures performed in the examination are standard procedures that have been performed frequently in other studies. While this project is assessing measurements in one population, there is limited threat to external validity because this is a project of instrument comparability and repeatability and is not intended to make generalizations about the population as a whole.

Data Analysis

Repeated measures analysis of variance (Repeated measures ANOVA) will be completed with measurement environment (single vision CL, center-distance CL, center-near CL). If differences are detected in lens type (center-distance, o center-near), a post-hoc analysis will take place.

Bibliography:

Berntsen, D.A. & Kramer, C.E. (2013). Peripheral defocus with spherical and multifocal soft contact lenses. *Optom Vis Sci*, 90, 1215-24.

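### Lens order is randomised at the Second Visit, but no masking is described for the three accommodation tests that rest on participant report or examiner judgement; coded lenses would be a cheap improvement

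*Combined protocol and SAP*

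**What the plan says.** At the Second Visit each participant repeats the baseline measurements, apart from dilation, with a center-distance and a center-near Biofinity multifocal, both with a +2.50 D add. On allocation the section says only "The order will be randomized for each participant". The document describes no masking of participant or examiner, no coding of the lenses and no concealment of the sequence. The Internal Validity section states "There are no threats to internal validity".

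The Measurement section makes accommodation the primary measurement and lists four techniques without ranking them:

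- Objective amplitude: "The refractive power of the eye will be measured with the Grand Seiko autorefractor".
- Subjective amplitude (called push-up in the Baseline Exam list): "The participant will be instructed to report the moment when the letters first become blurred".
- Accuracy (MEM): "A handheld light and loose trial spectacle lenses are used to quantify the focusing position of the eye".
- Facility: "Once the participant clears the letters, they will state" that they are clear, and the examiner then turns the flipper.

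Background and Rationale reports a general view that center-near designs give the most accommodative relief. It adds that "it is reasonable to hypothesize that center near multifocal contact lenses may provide a greater therapeutic effect for accommodative and binocular vision disorders". The comparator in that sentence is printed as center near again, but the reasoning shows that center-distance is meant.

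**The concern.** Randomising the order of two lenses within a visit protects their comparison from practice and fatigue, because each lens comes first about equally often. It does not protect against expectation. If the participant or examiner knows which design is on the eye and expects it to behave in a certain way, the effect goes with the lens in whichever position it is worn. Averaging over orders leaves it intact.

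Three of the four techniques have a human judgement at the point of measurement: the moment of blur, the moment of clarity, and the reading of the retinoscopy reflex. The contrast at stake is the one named in Study Objectives, center-near against center-distance. Data Analysis plans a repeated measures ANOVA without naming a lead outcome, so the plan does not set these three tests below the autorefractor. It also gives no reason for accepting the risk, since Internal Validity says there is none.

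**Working it through.** **1. Exposure of each technique, from the Measurement section**

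| Technique | Who determines the value | Exposure to expectation |
|---|---|---|
| Autorefractor amplitude | Instrument | Low; participant effort can still matter |
| Push-up amplitude | Participant's report | Yes |
| Facility | Participant's report, examiner-run | Yes |
| MEM | Examiner's reading | Yes |

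**2. The plan's own sample size**

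Inputs from the Sample section: difference 0.5 D, SD 0.53 D, power 90%, required n = 14, enrolled n = 14 + 6 = 20. The significance level and the test are not stated; I assume two-sided 0.05 and a paired t-test, with 0.53 D as the SD of the within-participant difference.

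Rejection probability = P(|T| > t(0.975, n−1)), where T is noncentral t with n−1 degrees of freedom and noncentrality λ = δ√n / SD.

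- n = 14: λ = 0.5 × √14 / 0.53 = 3.53, power 90.3%.
- n = 13: power 87.7%.
- n = 20: power 97.9%.

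The stated 14 is reproduced. Masking does not change it.

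**3. Illustration of an expectation shift**

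The documents give no bias size, so the shift b is an assumption. With no true difference and n = 20, put δ = b in the same formula: λ = b√20 / SD. For example, b = 0.1 D and SD 0.53 D give λ = 0.1 × 4.472 / 0.53 = 0.84. The SD is varied as well, because 0.53 D comes from published objective measurements and the documents give no SD for push-up or MEM.

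| Assumed shift b | b as share of the 0.5 D target | SD 0.53 D | SD 0.75 D | SD 1.0 D |
|---|---|---|---|---|
| 0 | 0% | 5.0% | 5.0% | 5.0% |
| 0.1 D | 20% | 12.6% | 8.8% | 7.1% |
| 0.2 D | 40% | 36.1% | 20.5% | 13.6% |
| 0.3 D | 60% | 67.1% | 39.7% | 24.7% |

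Entries in the last three columns are probabilities of p < 0.05. The test is two-sided, so they are the same whichever lens the shift favours. The table applies only to outcomes in dioptres. Facility is counted per minute and would need its own scale.

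**The case against.** Several points on the other side stand.

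- The documents are silent on masking; they do not say that participants are told the design. The consent text was not available for this review, so what participants learn cannot be checked.
- A reader might infer that participants come from an optometry college and know the designs. The recruitment list does not support that. Emails go to the whole university, and other routes are flyers, a university advertisement and calls to soft-lens wearers identified from clinic records. Only word of mouth is tied to the College, and it includes visitors. Prior multifocal wear is excluded, so participants have no wearing experience of either design.
- The hypothesis favouring center-near concerns treatment of accommodative and binocular vision disorders, which the eligibility criteria exclude. The stated objective has no direction, and no direction is given for push-up, MEM or facility in healthy eyes. The background still shows which design the study team thinks gives more relief.
- The sample size rests on objective data, and the technique closest to those data is the least exposed.
- A reader might infer that coding the lenses removes the bias for everyone. It does not. The examiner can be masked only if someone else prepares the lenses, and the documents say nothing about staffing. An examiner may also recognise the design at retinoscopy, and participants may notice visual differences. The single-vision condition, part of the planned ANOVA, is always measured at baseline and stays unmasked.

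These points limit both the likely size of the problem and the benefit of the fix. They do not answer the central one: randomised order does nothing about expectation, and no other safeguard is described for three of the four techniques.

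**Conclusion.** The point holds as a cheap improvement to the design; it does not show that the trial is invalid. As written, the center-near versus center-distance contrast on push-up amplitude, facility and MEM is open to expectation effects, and the statement on internal validity is too strong. The autorefractor contrast is much less affected.

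The size is unknown. The false-positive ranges, 13% to 67% at a paired SD of 0.53 D and 7% to 25% at 1.0 D for shifts of 0.1 to 0.3 D, rest on assumed shifts, n = 20, a two-sided 0.05 paired t-test and no true difference. They show that a shift well below the 0.5 D target could matter. They are not an estimate of what will happen here, and the 67% figure in particular pairs the largest assumed shift with the smallest SD considered.

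**What to change.** Add to the Second Visit section:

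- The two Biofinity multifocals, with the same +2.50 D add, are presented under codes A and B from the randomisation list, including for the autorefraction set-up in which the multifocal is on the left eye only.
- Participants are not told which design they are wearing until their testing is complete.
- Where an existing team member can prepare the lenses, the examiner is not told either. Otherwise the protocol states that the examiner is unmasked.

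In Internal Validity, replace the sentence "There are no threats to internal validity" with the limits that remain: an examiner who may be unmasked or may recognise the design at retinoscopy, and a single-vision condition that is always measured at baseline and unmasked.

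Cost: a coded list, labelled lenses and minor preparation time. Withholding the design from participants needs no additional staff, visit or procedure, and the sample size stays at 20. Masking may be incomplete, most likely for MEM. The documents contain no cost or staffing information, so calling this cheap is a judgement based on the two lenses sharing brand and add and being tested at one visit.

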Title Page

Study Title: *Accommodative Behaviors in Multifocal Contact Lenses*

NCT Number: 06064617

Date of Document: Approved by IRB on Nov 30, 2023, Uploaded to Clinical Trials.gov on 08/18/2025

Research Protocol

Accommodative Behaviors in Multifocal Contact Lenses

Study Objectives:

The purpose of this study is to determine if accommodation differs with center near and center distance multifocal contact lenses

Background and Rationale:

Soft multifocal contact lenses are used for a variety of reasons in patient care. Multifocal contact lenses are most often used to correct presbyopic vision by providing a range of clear vision at both distance and near (Chu and Huang, 2010). Multifocal contact lenses correct vision at different distances by introducing a power gradient over the eye. They are designed using center near or center distance designs. For center near designs, the near addition is placed in the center of the lens, and the power becomes more negative in the periphery. Conversely, for center distance designs, the distance prescription is placed in the center, and the power of the lens becomes more positive in the periphery in order to provide the near addition. Center near and distance designs have varying advantages and disadvantages for presbyopic vision correction, so a fitter may choose a specific design based on a patient's individual visual needs. Generally, it is thought that center near designs provide the most accommodative relief and superior near vision because the near addition is centered in the pupil and able to allow maximum near correction, even with miotic pupil size changes associated with accommodation.

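### Single vision is measured only at the first visit, so the three-lens ANOVA cannot separate lens from visit; the protected center-near versus center-distance contrast is not named as primary

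*Combined protocol and SAP*

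**What the plan says.** **Objective and sample size.** Study Objectives sets out to "determine if accommodation differs with center near and center distance multifocal contact lenses". The Sample section sizes the study for the same comparison: "In order to detect a 0.5 D difference in accommodative amplitude between center-distance and center-near contact lenses with 90% statistical power", giving 14 participants, with 20 to be enrolled.

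**Schedule.** Detailed Study Procedures describes "a baseline visit, and then a second visit on another day with center-distance and center-near contact lenses". Under Second Visit, "participants will repeat measurements completed at the first examination (except for dilation/cycloplegia) with a center-distance and center-near Biofinity multifocal contact lens", followed by "The order will be randomized for each participant". Randomised order is mentioned only there, and no single-vision condition is listed for that visit.

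**Analysis.** The Data Analysis section has two sentences: "Repeated measures analysis of variance (Repeated measures ANOVA) will be completed with measurement environment (single vision CL, center-distance CL, center-near CL", and then "If differences are detected in lens type (center-distance, o center-near), a post-hoc analysis will take place". It names no primary contrast, multiplicity method, or term for visit, period or sequence.

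**Validity.** The Internal Validity section opens with "There are no threats to internal validity".

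**The concern.** Every single-vision measurement comes first and on a different day from every multifocal measurement. Any change between days, such as practice with the push-up or flipper test, fatigue, or ordinary day-to-day variation, falls entirely on the single-vision versus multifocal differences. It could then be reported as a lens effect.

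The comparison the study was designed for escapes this, because both multifocals are tested at the second visit. Yet it is not singled out. It is reached through a post-hoc step whose opening condition is unclear: a significant three-level test, or a center-distance versus center-near difference. The route to the main result could be chosen after the data are seen. The randomised order is also left out of the analysis.

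**Working it through.** CD = center-distance, CN = center-near, SV = single vision.

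**Inputs from the protocol.** n = 20; target difference 0.5 D; SD 0.53 D; planned power 90%.

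**Assumptions.** Two-sided alpha 0.05 (none is stated). The 0.53 D is read as the SD of a paired difference and applied to all three lens pairs. Visit shift, order effect and extra between-day SD are not in the documents, so ranges are shown. That baseline accommodation is measured in single-vision lenses is inferred: the sphere lens is named only for the refractive error assessment, but the ANOVA's single-vision level has no other source.

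**1. The plan's own figure.** For a paired t-test the noncentrality is (0.5/0.53)·√n. At n = 14 it is 3.53 and power is 0.903; at n = 13 power is 0.877. The stated 14 is reproduced. At n = 20 the noncentrality is 4.22 and power is 0.979.

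**2. Visit shift with no lens effect.** The condition means are (0, v, v), and their squared deviations sum to 2v²/3. The error variance is 0.53²/2 = 0.14045. The omnibus noncentrality is therefore 20 × (2v²/3)/0.14045 on 2 and 38 df; at v = 0.2 D it is 3.80. Each SV contrast has noncentrality (v/0.53)·√20 on 19 df.

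| Visit shift (D) | Omnibus rejects | Each SV contrast rejects (unadjusted) | Direct CD-CN rejects |
|---|---|---|---|
| 0 | 5% | 5% | 5% |
| 0.1 | 12% | 13% | 5% |
| 0.2 | 37% | 36% | 5% |
| 0.3 | 71% | 67% | 5% |
| 0.4 | 93% | 89% | 5% |

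The shift cancels from CD-CN, so that test keeps its 5%. If it is also gated on the omnibus test, its error is 5% or less.

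**3. Cost of the gate when CD-CN is truly 0.5 D** (simulation, 40,000 runs). With SV equal to CD, gated unadjusted power is 0.977, 0.979, 0.979 and 0.958 at visit shifts of 0, 0.25, 0.5 and -0.25 D, against 0.979 ungated. Over four assumed positions of the SV mean:

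- No extra between-day SD: 96-98% unadjusted, 93-95% with Bonferroni. The ungated test at 0.05/3 has 93%.
- Extra between-day SD of 0.25 D: 92-98%.
- Extra between-day SD of 0.5 D: 84-95% with a pooled error term in the post-hoc test, 87-98% with the contrast's own error term.

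**4. Omitting the period term** (simulation, 40,000 runs). The order effect is the second-lens-minus-first-lens shift. Power for 0.5 D:

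| Order effect (D) | No term, simple randomisation | No term, 10:10 | Type I error, no term, 10:10 |
|---|---|---|---|
| 0 | 98% | 98% | 5% |
| 0.1 | 98% | 98% | 4.5% |
| 0.25 | 95% | 96% | 3% |
| 0.5 | 83% | 89% | 0.8% |

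With the term, power is 97-98% throughout. Without it, type I error under simple randomisation stays near 5% averaged over allocations. Under 10:10 the test becomes conservative, because the order effect inflates the estimated SD although it cancels from the mean.

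**5. Chance imbalance.** The randomisation method is not stated. If it is simple, a 7:13 or worse split has binomial probability 0.263. Without a period term, 7:13 shifts the CD-CN estimate by order effect × (13 − 7)/20; for 0.25 D that is 0.25 × 0.3 = 0.075 D.

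**The case against.** **The study's own question is unharmed.** CD versus CN is compared within one visit in randomised order, keeps its type I error, and has 98% power against a planned 90%. Single vision is in neither the objective nor the sample-size target. This stands, and it limits the seriousness of the point.

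**The post-hoc sentence names only CD and CN**, so it could mean that those two are compared before any post-hoc step. That reading is possible. However, the only test described before that step is the three-level ANOVA, and on either reading no primary contrast is named.

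**The rejection rates are at the high end.** They assume no extra between-day variance and no multiplicity adjustment. At a 0.2 D shift, the 36% for a single-vision contrast falls to 31% or 22% with an extra between-day SD of 0.25 or 0.5 D, or to 20% at alpha 0.05/3. At 0.4 D, the 89% falls to 83%, 64% or 77%. Nothing in the documents shows which shift is realistic. This changes the size, not the aliasing, which needs no assumed number.

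**The period term matters little.** Power without it stays at or above 95% up to an order effect of 0.25 D and falls below 90% only at 0.5 D, as large as the target itself. This is fair; it is the lesser part of the point.

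**Relabelling does not remove the confounding.** That is correct. No model can, because single vision is never measured at the second visit.

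**Conclusion.** The concern holds and the plan should be changed. By the protocol's own schedule, lens and visit are fully aliased in both single-vision contrasts and so enter the omnibus test; the Internal Validity statement is therefore wrong. How often a false multifocal effect would be declared depends on the unknown visit shift. Under the stated assumptions, the omnibus rate runs from 12% at 0.1 D to 93% at 0.4 D.

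CD versus CN is not biased by visit, and the sample size is not in error. For that contrast the defects are the missing primary designation, an ambiguous gate, and an unused randomised order. They cost flexibility and some precision rather than validity. Gated power falls below 90% in some scenarios only at the larger assumed between-day SD of 0.5 D.

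**What to change.** 1. Name CN minus CD as the primary contrast. Test it at two-sided 0.05 on the two second-visit conditions, with fixed lens, period and sequence and random participant (equivalent to the 2×2 crossover t-test), not conditional on a three-level omnibus test.
2. Allocate order in balanced form, 10 participants per sequence, and keep the period term, because balance without it makes the test conservative.
3. Report the single-vision contrasts as secondary and descriptive, each with its own error term, labelled non-randomised and confounded with visit. If they are meant to support a lens conclusion, single vision must be measured again at the second visit within the randomised order. That adds testing to a visit capped at 90 minutes.
4. Replace the Internal Validity claim with a statement that single vision is measured at baseline only, so contrasts with it are confounded with visit, while CN and CD are compared within the second visit in randomised order.

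Items 1, 2 and 4, and the labelling in item 3, need only revised wording and a balanced order list: no extra participants, visits or measurements. The statistical cost is one degree of freedom. With no order effect, power for 0.5 D goes from 98.0% to 97.9% (balanced) or 97.2% (simple). The single-vision comparisons lose any confirmatory role.

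### The ANOVA names lens as its only factor, and the plan does not say how readings at several demands become the powered accommodative amplitude or which comparison counts

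*Combined protocol and SAP*

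**What the plan says.** The Data Analysis section plans a repeated measures ANOVA that "will be completed with measurement environment (single vision CL, center-distance CL, center-near CL". If lens type differs, "a post-hoc analysis will take place". It names no outcome variable, demand factor, lens-by-demand term, significance level or multiplicity rule.

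The Measurement section opens with "The primary measurement of interest is accommodation, which will be quantified using the following techniques" and lists four techniques. Of the first, Objective Accommodative Amplitude, it says: "This non-invasive technique quantifies the total focusing ability of the eye using methods that are commonly used clinically". Readings are taken at "multiple stimulus positions (ranging from optical infinity to 20cm", but the distances then listed for assessing accommodation are "2.5 D (40 cm), and 4 D (25 cm), and 5 D (20 cm". It adds: "Ten repeated measures will be collected at each stimulus position".

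The Baseline Exam schedule says of the autorefractor: "Refractive Error will be measured at several points". Its list has four entries: 0, 2.5, 4 and 5 D. The Second Visit section repeats the baseline measurements, other than those under dilation, with both multifocal designs.

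The Sample section powers the study at 90% for a 0.5 D center-distance versus center-near difference in accommodative amplitude. It takes the SD of 0.53 D from a published comparison of center-distance with single-vision lenses, finds 14 participants sufficient and enrolls 20.

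**The concern.** Each participant supplies a grid of objective readings: three lenses by three demands, or by four if 0 D is counted. The stated model covers only the lens dimension. An analyst could take the response at 5 D, the largest response, the change from 0 D, a mean over demands, or a separate ANOVA at each demand. Each is compatible with the text, and they differ in power and in false-positive risk.

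The powered 0.5 D is tied to no demand. A difference found at any one demand could therefore be presented as the result for which the study was sized, and a choice made after seeing the data would leave the reported p-value hard to interpret.

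**Working it through.** **Inputs from the documents.** Difference 0.5 D, SD 0.53 D, power 90%, n = 14 required and 20 enrolled (Sample); near demands 2.5, 4 and 5 D (Measurement).

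**Assumptions, not in the documents.** Two-sided 5% level; SD 0.53 D for the paired lens difference at every demand; a common correlation r between demands; in steps 3 and 4, a lens effect proportional to demand.

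**1. The plan's own figure.** Paired t-test with noncentrality (d/SD)·√n. With d = 0.5 and SD = 0.53, n = 13 gives 87.7% power and n = 14 gives 90.3%, so the stated 14 is reproduced. At n = 20 the noncentrality is (0.5/0.53)·√20 = 4.22 and power is 97.9%. This is for one contrast on one amplitude value per lens.

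**2. A separate unadjusted test at each near demand.** If the tests are independent, the family-wise error is 1 − 0.95³ = 14.3%. Simulating a three-lens repeated measures ANOVA at each demand with n = 20 and no lens effect gives about 14% to 15% for r = 0, 13% for r = 0.5 and 10% for r = 0.8.

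**3. One demand chosen as the outcome, n = 20.** Setting 0.5 D at 5 D gives 0.5 × 2.5/5 = 0.25 D at 2.5 D and 0.5 × 4/5 = 0.40 D at 4 D.

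| Demand | Effect | Noncentrality | Power |
|---|---|---|---|
| 2.5 D | 0.25 D | 2.11 | 52% |
| 4 D | 0.40 D | 3.38 | 89% |
| 5 D | 0.50 D | 4.22 | 98% |

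**4. Mean over the three near demands, n = 20.** The mean effect is (0.25 + 0.40 + 0.50)/3 = 0.383 D, and the SD of the mean is 0.53·√((1 + 2r)/3).

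| r | SD of mean | Power |
|---|---|---|
| 0.3 | 0.387 D | 98.7% |
| 0.5 | 0.433 D | 96.4% |
| 0.8 | 0.493 D | 90.9% |

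If the effect is instead 0.5 D at all three near demands, the same SDs give at least 99.0% power, above the 97.9% for one demand alone.

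**5. Adjusted tests at each near demand.** Bonferroni over three demands uses 0.05/3 = 0.0167. For a 0.5 D effect at the demand tested, power at n = 20 is 93.3%.

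**The case against.** The strongest reply is that the plan aims at an amplitude. The Measurement section gives the objective technique that name and says it captures total focusing ability, and the Sample section powers an amplitude difference. One amplitude per participant and lens fits a one-factor, three-level ANOVA, with no pooling and no test per demand, and power at n = 20 is then 97.9%. The stated objective is only whether accommodation differs between designs, which a lens effect can answer.

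Much of this stands. A reader might infer that the one-factor model cannot handle these data properly, or that it forces a choice between diluting the effect and inflating false positives. The documents do not support either inference:

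- A single amplitude per lens avoids both costs.
- Pooling the three near demands keeps power above 90% in step 4.
- A marked loss needs a further assumption. With the proportional effect, averaging in 0 D lowers the mean effect to 1.15/4 = 0.2875 D and power to 92%, 83% or 70% for r = 0.3, 0.5 or 0.8. No section proposes that average, and the Measurement section's list of distances for accommodation omits 0 D.
- The plan is silent on adjustment; it does not say that tests will be unadjusted.

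What the reply does not supply is the rule that turns readings at three or four demands into an amplitude. Maximum response, response at 5 D, change from 0 D and a mean are all still open.

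**Conclusion.** The concern holds as a gap in specification with a better method at hand. Lens is the only factor named, demand has no stated role, the powered amplitude has no derivation and no comparison is named as decisive. Under the stated assumptions, power ranges from 52% to 99% according to the near demand or near-demand average used, and unadjusted testing at three demands raises the false-positive rate from 5% to about 10% to 15%.

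The power range rests on an assumed proportional effect and on an SD borrowed from a different lens comparison; it shows how much the choice can matter and does not forecast this study. The sample size is not in question here: 14 is reproduced, and 20 is ample for one well-defined 0.5 D contrast. It would be wrong to conclude that a one-factor analysis of a properly defined amplitude is invalid.

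**What to change.** For the objective response, replace the one-factor ANOVA with a repeated-measures or mixed model on the mean of the ten readings, with lens (three levels), demand (2.5, 4 and 5 D), lens by demand, and participant. Before the data are seen:

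- Name one primary center-distance minus center-near contrast, either at one stated demand or averaged over the three near demands, tested at two-sided 5%.
- Treat the per-demand contrasts as secondary, with a Bonferroni or Holm adjustment.
- Use the 0 D reading only as the reference, and do not average it into the outcome.
- Reconcile the demand lists in the Measurement and Baseline Exam sections.

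The cost is a few sentences of analysis plan, slightly more modelling and less freedom to claim a positive at any single demand. No extra participants or measurements are needed.
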